16.1.1 Plasma parameters

Part A and B (single dose)

Text symbol	Definition	Calculation
Concentrations and times		
C_{\max}	Maximum (peak) plasma concentration	Obtained directly from the concentration–time data.
t_{\max}	Time to reach maximum (peak) plasma concentration	Obtained directly from the concentration–time data.
Half-life		
λ_z	Terminal rate constant	Estimated by linear regression of logarithmically transformed concentration versus time data.
$t_{1/2}$	Terminal half-life	Calculated from the terminal slope of the log concentration–time curve, as follows: $t_{1/2} = \frac{\log_e 2}{\lambda_z}$
Areas under the curve		
AUC_{last}	Area under the plasma concentration–time curve from time zero to time of last measurable concentration	Calculated using the trapezoidal method.
AUC_{inf}	Area under the plasma concentration–time curve from time zero to infinity	Calculated using the trapezoidal method for the interval 0 to t_{last} (time t_{last} is the time at which the last non-zero level was recorded), plus the area under the

Text symbol	Definition	Calculation
AUC ₂₄	Area under the plasma concentration–time curve from time zero to time 24 h	exponential curve from t_{last} to infinity, calculated as follows: $AUC_{t-\inf} = \frac{\hat{C}_t}{\lambda_z}$ where \hat{C}_t is the predicted value of the concentration at t_{last} . Calculated using the trapezoidal method.
AUC ₇₂	Area under the plasma concentration–time curve from time zero to time 72 h	If λ_z is not estimable, a partial AUC is not calculated (when $t_{last} < t$). Calculated using the trapezoidal method.
%AUC _{extrap}	Percentage of AUC _∞ extrapolated from t_{last} to infinity	If λ_z is not estimable, a partial AUC is not calculated (when $t_{last} < t$). $\%AUC_{extrap} = \frac{100 \times AUC_{t-\inf}}{AUC_{\inf}}$
CL/F	Clearance, volume of distribution and mean residence time Apparent total clearance from plasma after oral administration	Calculated using the following formula: $CL / F = \frac{Dose}{AUC_{\inf}}$
V _z /F	Apparent volume of distribution during terminal phase after non-intravenous administration	Calculated using the following formula: $V_z / F = \frac{Dose}{\lambda_z \bullet AUC_{\inf}}$

Part C (multiple dose)

Day 1

Text symbol	Definition	Calculation
Concentrations and times		
C _{max}	Maximum (peak) plasma concentration	Obtained directly from the concentration–time data.
t _{max}	Time to reach maximum (peak) plasma concentration	Obtained directly from the concentration–time data.
Areas under the curve		
λ _z	Terminal rate constant	Estimated by linear regression of logarithmically transformed concentration versus time data.
t _{1/2}	Terminal half-life	Calculated from the terminal slope of the log concentration–time curve, as follows: $t_{1/2} = \frac{\log_e 2}{\lambda_z}$

Text symbol	Definition	Calculation
Areas under the curve (after final dose)		
AUC _{tau}	Area under the plasma concentration–time curve during a dosing interval (tau)	Calculated using the trapezoidal method.
AUC _{last}	Area under the plasma concentration–time curve from time zero to time of last measurable concentration	Calculated using the trapezoidal method.
AUC ₇₂	Area under the plasma concentration–time curve from time zero to time 72 h	Calculated using the trapezoidal method.
AUC _{inf}	Area under the plasma concentration–time curve from time zero to infinity	Calculated using the trapezoidal method for the interval 0 to t _{last} (time t _{last} is the time at which the last non-zero level was recorded), plus the area under the exponential curve from t _{last} to infinity, calculated as follows: $AUC_{t-\inf} = \frac{\hat{C}_t}{\lambda_z}$ where \hat{C}_t is the predicted value of the concentration at t _{last} . $\%AUC_{extrap} = \frac{100 \times AUC_{t-\inf}}{AUC_{\inf}}$
%AUC _{extrap}	Percentage of AUC _∞ extrapolated from t _{last} to infinity	

Days 2–14

Text symbol	Definition	Calculation
Concentrations during and after multiple dosing		
C _{trough}	Trough plasma concentration	Trough plasma concentration (measured concentration at the end of a dosing interval at steady state [taken directly before next administration]) obtained directly from the concentration–time data.

Final dosing day

Text symbol	Definition	Calculation
Concentrations and times (after final dose)		
C _{max}	Maximum (peak) plasma concentration	Obtained directly from the concentration–time data.
t _{max}	Time to reach maximum (peak) plasma concentration	Obtained directly from the concentration–time data.
Half-life (after final dose)		
λ _z	Terminal rate constant	Estimated by linear regression of logarithmically transformed concentration versus time data.
t _{1/2}	Terminal half-life	Calculated from the terminal slope of the log concentration–time curve, as follows: $t_{1/2} = \frac{\log_e 2}{\lambda_z}$

Text symbol	Definition	Calculation
Areas under the curve (after final dose)		
AUC _{tau}	Area under the plasma concentration–time curve during a dosing interval (tau)	Calculated using the trapezoidal method.
AUC _{last}	Area under the plasma concentration–time curve from time zero to time of last measurable concentration	Calculated using the trapezoidal method.
AUC ₇₂	Area under the plasma concentration–time curve from time zero to time 72 h	Calculated using the trapezoidal method.
AUC _{inf}	Area under the plasma concentration–time curve from time zero to infinity	Calculated using the trapezoidal method for the interval 0 to t _{last} (time t _{last} is the time at which the last non-zero level was recorded), plus the area under the exponential curve from t _{last} to infinity, calculated as follows: $AUC_{t-\inf} = \frac{\hat{C}_t}{\lambda_z}$ where \hat{C}_t is the predicted value of the concentration at t _{last} . $\%AUC_{extrap} = \frac{100 \times AUC_{t-\inf}}{AUC_{\inf}}$
Clearance, volume of distribution and mean residence time (after final dose)		
CL _{ss/F}	Apparent total clearance from plasma at steady state after non-intravenous administration	Calculated using the following formula: $CL_{ss} / F = \frac{Dose}{AUC_{tau}}$
V _{z/F}	apparent volume of distribution after non-intravenous administration calculated at steady state	Calculated using the following formula: $V_z / F = \frac{Dose}{\lambda_z \bullet AUC_{tau}}$
Accumulation and time invariance ratios		
R _{ac(AUC)}	Accumulation ratio for AUC	Calculated from AUC _{tau} at steady state and AUC _{tau} after a single dose
R _{ac(C_{max})}	Accumulation ratio for C _{max}	Calculated from C _{max} at steady state and C _{max} after a single dose
SR _(AUC)	Stationarity ratio for AUC	Stationarity ratio will be calculated from AUC _t at steady state and AUC _∞ after single dose $SR_{AUC} = \frac{AUC_t}{AUC_{\infty}}$

16.1.2 Urine sample parameters (Parts B and C)

Text	Symbol	Definition	Calculation
Urinary recovery			
Ae ₇₂		Cumulative amount of unchanged drug excreted into the urine at 72 h	Calculated as the sum of the products of concentration and urine volume over the appropriate collection intervals
Renal clearance			
CL _R		Renal clearance of drug from plasma	Calculated from the ratio of the appropriate values for urinary recovery and area under the plasma concentration–time curve, using the following formula:
			$CL_R = \frac{Ae_{24}}{AUC_{24}}$

16.2 Statistical methods

16.2.1 Planned analyses

Final statistical analysis, including analysis of PK parameters, will be done by HMR. A statistical analysis plan will be prepared by the HMR Statistics and Data Management Department after completion of the final protocol and before database lock.

All statistical analysis and reporting will be done using SAS 9.4 or higher.

16.2.2 Statistical hypotheses

The trial is an exploratory one, and there are no null hypotheses to be tested.

16.2.3 Analysis populations

The following populations will be identified:

Safety population: All subjects who received at least one dose of study drug.

PK concentration population: All subjects who received at least one dose of study drug and for whom a pharmacokinetic sample has been analysed.

PK parameter population: All subjects in the PK concentration population for whom pharmacokinetic parameters can be derived.

In all populations, treatment will be assigned based upon the treatment subjects actually received, regardless of the treatment to which they were randomised.

The primary endpoint will be analysed using the safety and PK populations.

16.2.4 General considerations for data analyses

The minimum set of summary statistics for numeric variables will be: n, mean, standard deviation (or standard error), median, minimum, and maximum. 95% confidence intervals (CI) will be presented where appropriate for data interpretation.

Categorical data will be summarised in frequency tables with n and percentage. Summaries of a categorical variable will include all recorded values.

The minimum and maximum values will be presented to the same number of decimal places as the raw data collected on the CRF (or to 3 significant figures for derived parameters). The mean, median and percentiles (eg Q1, and Q3) will be presented to one additional decimal place. The standard deviation and standard error will be presented to 2 additional decimal places.

‘Baseline’ will be the latest value obtained before IMP administration (predose on Day 1, or Day –1 if not recorded at predose, or screening if not recorded at predose or on Day –1. Out-of-range laboratory tests may be repeated. If a test is out of-range at baseline and repeated before dosing, the latest repeat value before dosing will be used as baseline. However, if a test is out-of-range and repeated at any other time during the study, the out-of-range value (not the repeat value) will be included in statistical summaries.

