9.4 Withdrawal of subjects from the trial

9.4.1 *Subject withdrawal*

Subjects are free to withdraw from the trial at any time without giving reasons. Furthermore, the investigator may withdraw a subject for reasons such as intolerance to trial medication, intercurrent illness, need for medication which is contraindicated, significant non-compliance with the requirements of the trial, or withdrawal of consent. The investigator will assess the reasons for withdrawal as far as possible and will fully record the circumstances and medical details.

Subjects will be informed before they agree to take part in the trial that, if they withdraw or are withdrawn:

- the investigator will stop collecting information about them; and
- they can ask the investigator to destroy any identifiable samples taken from them.

The investigator will ask withdrawn subjects to consent to a follow-up examination, to check that they have come to no harm as a result of taking part in the trial.

Provided that the subject agrees, they will undergo, at withdrawal from the trial (or as soon as possible afterwards), the standard medical examination and laboratory tests which they would have undergone had they completed it. The investigator will record in the case report form (CRF) the results of the follow-up examination of withdrawn subjects, if they give their consent for that.

9.4.2 *Individual subject stopping criteria*

A subject who meets any of the following criteria will receive no further doses.

- SAE considered related to study treatment.
- mean QTcF of > 500 msec or increase from baseline of > 60 msec
- $ALT \geq 5 \times ULN$.
- $ALT \geq 3 \times ULN$ and total bilirubin $\geq 2 \times ULN$ or international normalised ratio (INR) of ≥ 1.5 , as per the guidelines for acute liver failure. (If a subject meets that withdrawal criterion, serum bilirubin fractionation should be performed.)
- $ALT \geq 3 \times ULN$ if associated with the appearance or worsening of rash or hepatitis symptoms (fatigue, nausea, vomiting, right upper quadrant pain or tenderness, fever, rash or eosinophilia). Subjects who have $ALT \geq 3 \times ULN$ and $< 5 \times ULN$, and total bilirubin $< 2 \times ULN$, who do not exhibit hepatitis symptoms or rash, can continue in the study (and continue receiving trial

medication) as long as they can be monitored weekly until liver chemistries return to within baseline values.

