16.2.6.2 Clinical laboratory evaluations

Data from haematology and clinical chemistry will be summarised by treatment.

Any laboratory value outside the reference interval for that variable will be flagged with an 'H' if it is higher than the reference interval, and with an 'L' if it is lower. Additionally, if, during the course of the trial, a variable changes from baseline by more than a predetermined amount (as defined by the principal investigator), that value will receive a flag 'I' if increased, or 'D' if decreased. Therefore, if a value both falls outside the reference interval and alters from the baseline value by more than the predetermined amount, it will attract a double flag and will be considered to be potentially clinically important.

All laboratory values of potential clinical importance will be listed. In a separate listing, laboratory values of potential clinical importance will be listed with all related laboratory results (ie haematology or clinical chemistry). Frequencies of laboratory values of potential clinical importance will be summarised.

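### A post-dose laboratory repeat that is worse than the first value is left out of the potentially-clinically-important frequencies and the tabulated extremes

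*Combined protocol and SAP*

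**What the plan says.** Section 16.2.4 makes repeats optional: "Out-of-range laboratory tests may be repeated". It then treats them in two ways. Before dosing, "If a test is out of-range at baseline and repeated before dosing, the latest repeat value before dosing will be used as baseline". But if a test is out of range and "repeated at any other time during the study, the out-of-range value (not the repeat value) will be included in statistical summaries". The second rule does not depend on which way the repeat moved. The same section makes the minimum and maximum part of the standard set of statistics for every numeric variable.

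Section 16.2.6.2 plans two kinds of laboratory summary. One is descriptive: "Data from haematology and clinical chemistry will be summarised by treatment". The other is a count: "Frequencies of laboratory values of potential clinical importance will be summarised". A value is potentially clinically important (PCI) when it is both outside the reference interval and changed from baseline by more than an amount set by the principal investigator. The section also lists every PCI value, and lists PCI values again alongside all related results. It does not exclude repeats from either listing.

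**The concern.** The evident purpose of the post-dose rule is conservative: an abnormal finding should not disappear because a later sample was normal. Written without a condition, the rule does the reverse when the analyte is still moving away from normal. The milder value goes into the tables and the worse one does not.

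Laboratory safety tests are among the primary endpoints of Parts A and C (Section 7.2.1). In groups this small, one subject changes a frequency visibly. A reader who compares the PCI table with the PCI listing could find a subject in the listing whom the table does not count, or a listed value beyond the tabulated maximum.

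**Working it through.** The plan gives no figure on this point, so there is none to reproduce. The check applies the rule to the outputs planned in Section 16.2.6.2.

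**Inputs from the documents.** Six active and 2 placebo subjects per dose level in Parts A and C (Section 8.1). The PCI definition (Section 16.2.6.2). The repeat rule (Section 16.2.4). Entry requires ALT below 1.5 x ULN (exclusion criterion 22). ALT of at least 5 x ULN stops dosing (Section 9.4.2). The ALT values below are assumed for illustration; the predetermined amount is not stated.

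**Frequency table.** Suppose one active subject has a scheduled ALT of 1.2 x ULN, with a change below the predetermined amount, and the repeat is twice that: 1.2 x 2 = 2.4 x ULN, with a change above it.
- First value: out of range, change too small, not PCI.
- Repeat: out of range, change large enough, PCI.
- Count under the rule: 0/6 = 0%. Count on all values: 1/6 = 16.7%.
- The difference is 16.7 percentage points, provided that no later scheduled value for that subject is PCI.

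**Tabulated extremes.** Suppose a scheduled ALT is 3.2 x ULN and the repeat two days later follows a three-day doubling: 3.2 x 2^(2/3) = 5.1 x ULN. If no other value in the group is higher, the table shows a maximum of 3.2 x ULN while 5.1 x ULN was recorded. The PCI count probably does not change here. With an entry value below 1.5 x ULN, and a baseline still below that level, the first value is already a rise of more than 3.2 - 1.5 = 1.7 x ULN and is very likely PCI. This case therefore affects the extreme only.

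**How often a repeat is further out.** Assume no drug effect, normally distributed values, a reference interval holding the central 95%, and correlation r between two measurements in the same subject. Given that the first value is beyond one limit, the chance that the repeat is further out on the same side is

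½ x P(both beyond that limit) / 0.025.

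| r | P(both beyond one limit) | Share of repeats further out |
|---|---|---|
| 0.5 | 0.0046 | 9% |
| 0.7 | 0.0083 | about 16% |
| 0.9 | 0.0148 | 30% |

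A simulation of 2,000,000 subjects gave the same shares. The documents do not give r. These are shares of repeats that are worse, not shares that newly become PCI, which will be smaller. They show only that a worse repeat is not exotic.

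**The case against.** The strongest reply is that little is actually hidden, and most of it stands.

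- **Not lost to the study.** A reader might infer that a repeat meeting a stopping criterion goes uncounted altogether. The documents do not support that. Section 9.4.2 acts on the subject: "A subject who meets any of the following criteria will receive no further doses". Under Section 14.2, a result that leads to withdrawal or a change of dose is reported as an adverse event, and if treatment-emergent it reaches the tables of Section 16.2.6.1. The Safety Review Group reviews laboratory safety tests under Section 8.5.1, and the PCI listings have no exclusion for repeats.
- **No demonstrated spurious rise from baseline.** A reader might also infer that replacing baseline values by repeats, but never post-dose ones, makes abnormalities appear to increase with no drug effect. In the model above, with every out-of-range value repeated, the out-of-range rate is 0.93% to 2.96% at baseline against 5.0% post-dose (r from 0.5 to 0.9). With a quarter repeated, it is 3.98% to 4.49% against 5.0%. However, Section 16.2.6.2 plans no shift table and no comparison of out-of-range rates at baseline and after dosing. In the planned PCI count, simulated with a change threshold of 1 SD, within-subject shares of variance of 30%, 50% and 70%, and every value repeated, the effect is 2.02 - 1.73 = 0.29, 3.23 - 2.90 = 0.33 and 4.00 - 3.74 = 0.26 percentage points per analyte. That is about 0.02 subjects in a group of 6. Placebo subjects follow the same rule. Taking the latest pre-dose value as baseline is a defensible choice.
- **Later tests may catch it.** A persistent rise may be PCI at the next scheduled sample. This narrows the problem but does not remove it.
- **Another sentence may rescue the count.** Section 16.2.4 says that summaries of a categorical variable include all recorded values. This most naturally means all categories. If it means all measurements, it conflicts with the repeat rule and needs clarifying.

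None of this answers the narrow point: the frequency table and the extremes are statistical summaries, and the rule as written excludes the worse value from them.

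**Conclusion.** The point holds as a reporting fault. Applied as written, Section 16.2.4 can leave a subject out of the PCI frequency table when the repeat is the first PCI value and no later scheduled value is PCI, and it can make a tabulated extreme milder than the most extreme value recorded. One such subject in an active group of 6 is 17 percentage points. How often this will happen cannot be derived from the documents: it depends on how many out-of-range tests are repeated, on within-subject variation and on the unstated predetermined amounts. The conclusion assumes that the frequency table counts as a statistical summary under Section 16.2.4, which is the plain reading. It does not extend to subject protection during the trial, and it gives no reason to change the baseline rule.

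**What to change.** In Sections 16.2.4 and 16.2.6.2, and in the statistical analysis plan that Section 16.2.1 requires before database lock:

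1. Keep the first (scheduled) value for descriptive summaries by timepoint.
2. State that PCI frequencies and on-treatment maxima and minima use all post-dose values, including repeats and unscheduled tests, taking the worst per subject and analyte.
3. Clarify whether the sentence on categorical summaries refers to categories or to measurements.

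The baseline definition stays as it is.

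The cost is about two sentences of wording and minor programming, with no new data. The drawback is that PCI frequencies can only stay the same or rise, and may include transient values. In Parts A and C they should be read against placebo under the same rule, not against a single baseline value, bearing in mind that there are only 2 placebo subjects per dose level. Part B has no placebo, so its fed and fasted sessions should be handled by the same rule.

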16.2.5 Study population analyses

16.2.5.1 Disposition of subjects

The disposition of all subjects in the enrolled population will be summarised including: number of subjects randomised; number completing the study, by treatment; and number discontinued from the study.

All subjects who withdraw or are withdrawn from the study will be listed, by treatment, with the reason for withdrawal.

16.2.5.2 Demographic and baseline characteristics

Demographic and baseline characteristics (eg physical examination, vital signs and ECGs) will be summarised.

Subjects who take concomitant medication will be listed. All non-trial medication will be coded using the latest version of the World Health Organisation Drug Dictionary Enhanced (WHO DDE) current at the time of database lock.

16.2.5.3 Treatment compliance

Dates and times of dosing will be listed.

16.2.6 Safety data analyses

Summaries and listings of safety data will use the safety population.

16.2.6.1 Adverse events

AEs will be coded using the version of the Medical Dictionary for Regulatory Activities (MedDRA) current at the time of database lock.

All AEs will be listed.

A treatment-emergent adverse event (TEAE) is an AE that emerges during treatment (having been absent before treatment) or that worsens after treatment³⁹.

The number of subjects with at least one TEAE will be tabulated by actual treatment and MedDRA system organ class and preferred term.

For each of the following, the number of TEAEs and subjects with TEAEs will be summarised by actual treatment as follows:

- TEAEs, by system organ class and preferred term
- drug-related TEAEs, by system organ class and preferred term

Subjects with more than one TEAE will be counted only once, at the maximum causality, for each system organ class and preferred term. AEs with missing severity and/or causality will be treated as severe and possibly related, respectively.

AEs leading to withdrawal, deaths and other SAEs will be listed separately (fatal events will be listed separately from non-fatal events).

16.2.6.2 Clinical laboratory evaluations

Data from haematology and clinical chemistry will be summarised by treatment.

Any laboratory value outside the reference interval for that variable will be flagged with an 'H' if it is higher than the reference interval, and with an 'L' if it is lower. Additionally, if, during the course of the trial, a variable changes from baseline by more than a predetermined amount (as defined by the principal investigator), that value will receive a flag 'I' if increased, or 'D' if decreased. Therefore, if a value both falls outside the reference interval and alters from the baseline value by more than the predetermined amount, it will attract a double flag and will be considered to be potentially clinically important.

All laboratory values of potential clinical importance will be listed. In a separate listing, laboratory values of potential clinical importance will be listed with all related laboratory results (ie haematology or clinical chemistry). Frequencies of laboratory values of potential clinical importance will be summarised.

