13. Presence or history of drug or alcohol abuse, or intake of more than 14 units of alcohol weekly.
14. Habitual, regular use of tobacco and/or nicotine containing products (including e-cigarettes) within 3 months of screening, until the end of the study. Social smokers or vapers may be included in the study (at the discretion of the investigator) provided they can abstain from use of those products from 1 month before the study until the end of the study.
15. Habitual and heavy consumption of caffeinated drinks (> 8 cups of coffee or equivalent per day).
16. Mean blood pressure and pulse rate in supine position at the screening examination outside the ranges: blood pressure 90–140 mm Hg systolic, 40–90 mm Hg diastolic; pulse rate 40–100 beats/min.

One set of repeats in triplicate is permitted if the mean values are borderline (ie values that are within 5 mm Hg for blood pressure or 5 beats/min for pulse rate) or if requested by the investigator. Subjects can be included if the repeat mean value is within range.
17. Possibility that the volunteer will not cooperate with the requirements of the protocol.
18. Evidence of drug abuse on urine testing.
19. Positive test for hepatitis B, hepatitis C or HIV.
20. Loss of more than 400 mL blood during the 3 months before the trial, eg as a blood donor.
21. Objection by GP to volunteer entering trial.
22. AST, ALT, gamma-glutamyl transferase (GGT), or total bilirubin $\geq 1.5 \times$ ULN.

A repeat is allowed on one occasion for determination of eligibility.
23. QT, PR, or QRS value, measured at screening visit on 12-lead ECG, outside of the following ranges: QT value > 450 msec (men) or > 470 msec (women), using Fridericia's formula (QTcF) for correction; PR value outside the range 110–220 msec; QRS value > 120 msec.

TriPLICATE measurements will be made, and a mean value used to determine eligibility. A repeat (in triplicate) is allowed on one occasion for determination of eligibility.
24. Clinically significant findings on 24-hour Holter testing at screening as determined by the Investigator (Part A only).

25. Vegetarian or vegan, or unwilling to eat a high-fat breakfast including bacon (eg for personal or religious reasons) (Part B only).

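### The laboratory rule for potentially clinically important values ignores the direction of change, so values moving back towards the reference interval are counted with worsening ones

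*Combined protocol and SAP*

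**What the plan says.** Section 16.2.6.2 sets two flags that are assigned independently. The first concerns the reference interval: a value outside it "will be flagged with an 'H' if it is higher than the reference interval, and with an 'L' if it is lower". The second concerns change from baseline: if the change exceeds an amount set by the principal investigator, "that value will receive a flag 'I' if increased, or 'D' if decreased". The two are then combined. The rule applies "if a value both falls outside the reference interval and alters from the baseline value by more than the predetermined amount"; in that case "it will attract a double flag and will be considered to be potentially clinically important". These values are listed, listed again beside the related results, and counted: "Frequencies of laboratory values of potential clinical importance will be summarised".

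The size of the qualifying change is not given for any analyte. Section 16.2.4 foresees a baseline that is itself abnormal: "If a test is out of-range at baseline and repeated before dosing, the latest repeat value before dosing will be used as baseline". Criterion 22 in section 9.3 sets a numerical entry limit, exclusion at 1.5 × ULN or above, for four tests: "AST, ALT, gamma-glutamyl transferase (GGT), or total bilirubin". For the other analytes in Table 11, entry rests on the investigator's judgement of clinical relevance under criterion 2.

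**The concern.** The verb in the combining sentence is neutral. A change in either direction satisfies it, so the recorded I or D plays no part in deciding whether a value counts. Someone who starts well above the upper limit and falls substantially, but not quite into range, is counted exactly like someone who starts normal and rises above the limit.

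Other rules in the same plan do carry a direction. Under section 16.2.6.1 a treatment-emergent event must be new or must worsen. In section 16.2.6.3 the change part of the QTcF rule concerns increases only. The laboratory rule departs from this pattern without explanation.

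Laboratory tests are among the primary safety endpoints of Parts A and C (section 7.2.1). What is at stake is whether one table on that endpoint means what a reader will take it to mean. As written, its count mixes worsening with improvement.

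**Working it through.** The plan states no figure on this point, so there is nothing to reproduce. The check has three steps.

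**1. The rule taken literally.** Let b be baseline, v the later value, lo and hi the reference limits, and t > 0 the qualifying change. Then H: v > hi; L: v < lo; I: v − b > t; D: b − v > t. A value counts if it has H or L and also I or D. With arbitrary numbers lo = 10, hi = 40, t = 10:

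| Baseline | Later value | Flags | Counted | Movement |
|---|---|---|---|---|
| 25 | 45 | H, I | yes | out of range |
| 25 | 5 | L, D | yes | out of range |
| 56 | 45 | H, D | yes | towards range |
| −6 | 5 | L, I | yes | towards range (negative baseline for arithmetic only) |
| 45 | 46 | H | no | change too small |

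An H-with-D value has v > hi and b > v + t, so b > v > hi: baseline was further above the interval. By the same argument, L with I implies b < v < lo. Every opposite-direction pair is therefore a movement towards the interval from a worse start.

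**2. When it can arise for the four capped tests.** If baseline is below 1.5 × ULN and the later value is above 1 × ULN, the fall is less than 1.5 − 1 = 0.5 × ULN. H with D is then possible only if t is below 0.5 × ULN. For example, GGT falling from 1.4 to 1.1 × ULN changes by 0.3 × ULN and is counted only if t is below that. The cap applies at screening, whereas baseline is the latest pre-dose value, so a baseline above the cap is possible.

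**3. Illustration of size, all inputs assumed.** A standardised analyte, baseline and later value bivariate normal with equal means and variances, reference interval ±1.96 SD, no screening and no drug effect; 4 million pairs for each correlation.

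| Correlation | t (SD) | Same direction, % of values | Opposite direction, % of values | Opposite as % of double flags |
|---|---|---|---|---|
| 0.5 | 0.5 | 3.876 | 0.1436 | 3.57 |
| 0.5 | 1.0 | 2.870 | 0.0340 | 1.17 |
| 0.5 | 1.5 | 1.756 | 0.0064 | 0.36 |
| 0.7 | 0.5 | 3.037 | 0.2377 | 7.26 |
| 0.7 | 1.0 | 1.694 | 0.0457 | 2.63 |
| 0.7 | 1.5 | 0.665 | 0.0055 | 0.82 |
| 0.85 | 0.5 | 1.937 | 0.2669 | 12.11 |
| 0.85 | 1.0 | 0.550 | 0.0269 | 4.67 |
| 0.85 | 1.5 | 0.074 | 0.0014 | 1.82 |

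The last column is opposite ÷ (same + opposite); for example 0.2669 ÷ (1.937 + 0.2669) = 12.11%. Screening would remove some of the extreme baselines on which opposite-direction pairs depend.

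**The case against.** The best defence is that this is an inclusive screen, not a verdict on harm. In a first-in-human trial, a large movement in an abnormal analyte may deserve a look whichever way it goes. The flag letters keep the direction, so listings that show them let a reader pick out improving values. Haematology and chemistry are also summarised by treatment, and clinically significant results can become adverse events under section 14.2. The SAP is still to be written (section 16.2.1) and could separate the pairs. All of this stands, and it limits the point to the frequency table. It does not supply the missing direction in that table.

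A reader might go further and infer three things that the documents do not support.

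- *That improving values are reported as toxicity or as a safety signal.* The plan's term is potentially clinically important, which marks values for attention.
- *That this count is the only per-subject laboratory outcome, so that one improving subject moves a dose group by 1/6 (17 percentage points) or a placebo pair by 1/2 (50 points).* The text counts values, not subjects. It does not say that placebo is tabulated by cohort, and it plans other laboratory outputs.
- *That escalation or stopping decisions could be distorted.* The criteria in sections 8.4 and 9.4.2 do not refer to this count, and the Safety Review Group reviews the laboratory tests themselves (section 8.5.1).

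It might also be argued that residence on standard meals without alcohol makes improvement likely. That is plausible, but the documents hold no data on it.

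**Conclusion.** The point holds as a defect of definition. Section 16.2.6.2, read as written, puts H-with-D and L-with-I values into the same frequency as worsening values, and no other section corrects this. That conclusion rests on the text alone.

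The size is a different matter. It depends on the change thresholds and on how many volunteers have an out-of-range baseline, and the documents give neither. The illustrative range of about 0.4% to 12% of double flags (about 0.001% to 0.27% of all values) depends entirely on its assumptions and suggests a small effect. The trial tests no hypotheses (section 16.2.2), so the consequence is a descriptive count that is less clear than it should be. It is worth correcting because correction is nearly free and the SAP is not yet final.

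**What to change.** In section 16.2.6.2, or in the SAP that section 16.2.1 says will be prepared before database lock, define potentially clinically important for the frequency summary as H together with I, or L together with D. Keep H-with-D and L-with-I values in the listings, with their flag letters shown, and give them a separate row in the frequency table. This preserves the inclusive screen while keeping the two directions apart.

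The cost is one sentence, a line of code and a slightly longer table. No assessment, sample or dosing rule is affected.
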